The *long term goal* of the PI's research group is to alleviate urinary symptoms as a contributor to disability among Veterans with PD and contribute to understanding of the brain-bladder connection in the setting of neurodegenerative disease. We propose the following specific aims:

Specific Aim #1: Using a RCT, determine non-inferiority of pelvic floor muscle exercise-based behavioral therapy versus drug therapy for urinary symptoms in PD. We hypothesize that pelvic floor muscle exercise-based behavioral therapy will reduce urinary symptom severity with a difference compared to

drug therapy that does not exceed the non-inferiority margin of a validated OAB questionnaire. The primary outcome, OAB severity, will be measured using the OAB symptom questionnaire (International Consultation on Incontinence-OAB (ICIQ-OAB) symptom score) with a non-inferiority margin of 15%.

Specific Aim #2 (mechanistic aim): Determine if domain-specific cognitive function impacts the response to exercise-based behavioral therapy or drug therapy for urinary symptoms.

Aim 2.a. Do higher baseline motor skill learning capacity and executive function scores predict better outcomes in the exercise-based behavioral therapy versus drug therapy group?

Aim 2.b. Compared to exercise therapy, does anticholinergic drug treatment for urinary symptoms worsen executive function and PD motor symptom severity?

Research Design and Methods

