We propose a three-site, RCT conducted at the Atlanta (lead site), Birmingham and Richmond VA medical centers to establish non-inferiority of pelvic floor muscle exercise-based behavioral therapy compared to drug therapy for urinary symptoms in adults with PD. Groups will be stratified by OAB symptom severity, PD motor symptom severity, gender, and site. We will randomize 90 participants in order to complete the study in 80 participants, assuming 85% power and a non-inferiority margin for the OAB symptom score of 15% at 12-weeks. **The primary outcome measure will be urinary symptom severity as measured by the ICIQ-OAB symptom score^{32,33}** collected at 3 time points during the study: baseline, 6 weeks, and 12 weeks. PFME-based behavioral therapy will occur over 3 visits conducted during the first 6 weeks as was performed in the BETTER2 PD study. Participants in the drug therapy group will also have 3 visits during the first 6 weeks in order to individually titrate solifenacin drug therapy according to a validated symptom scale. Solifenacin has been selected because this bladder-selective anticholinergic drug (less risk of cognitive side effects) is the only drug with published evidence of potential efficacy in PD³⁴. At baseline, randomized participants will undergo a brief neuropsychological battery adapted from our current study to assess cognitive factors that may predict a preferred treatment strategy. At the 12-week assessment, the brief neuropsychological battery and MDS-UPDRS will be repeated in order to assess any change associated with treatment allocation. Follow-up visits will occur at weeks 4 and 8 to ascertain side effects and assess treatment adherence.

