1. The **SRTT** is a task of motor procedural learning in which participants are asked to press one of four keys on a response box which correspond to a lighted stimulus⁴⁹. Unknown to the participant, the light stimuli occur in a sequence and thus reaction time improves as the participant performs multiple blocks of the sequenced-based task. This learning is demonstrated by an increase in reaction time when the stimuli are presented in a random order after repetitions of the sequenced-based task. The task is typically measured in millisecond response times. The SRTT can be administered in approximately 30 minutes and has been used in multiple studies of procedural learning among PD participants^{50,51}. A response box for the SRTT is available for purchase from Psychology Software Tools Inc. The software to collect, store, and analyze the SRTT reaction times is also available for purchase from this company. A standard operating system installed on a laptop computer is sufficient to allow for data collection and initial analysis of reaction time. Once reaction times for the sequenced and random blocks have been calculated, these data will be entered into the Redcap database.
2. The **CERAD Word List subtest**⁵² requires the subject to recall 10 words that are presented over three trials, followed by short-delay recall and recognition memory. Left entorhinal cortex volume is significantly correlated with immediate recall on this task⁵³.
3. The **Nonverbal/Spatial Selective Reminding Test**⁵⁴ taps spatial memory by requiring the subject to recall a dot pattern. Performance on this measure has been found to discriminate patients with right versus left temporal lobe epilepsy⁵⁵.
4. The **Wisconsin Card Sorting Test**⁵⁶ will be used to assess hypothesis generation and response shifting. Perseverative errors on this task are related to the volume of prefrontal cortex and frontal white matter hyperintensities in adults 50-81 years old^{57,58}. Perseverative errors will be residualized on the total number of errors to control for overall level of performance.
5. The **Subject Ordered Pointing Task** will assess working memory. Subject Ordered Pointing is sensitive to middorsolateral prefrontal cortex lesions in monkeys and humans, and activates dorsolateral prefrontal cortex on positron emission tomography in normal adults.

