Randomization: At the second visit, eligible participants will be randomized to one of two groups: treatment with PFME-based behavioral therapy or solifenacin drug therapy. Participants will be stratified by site, gender, UI severity (< or \geq a score of 9 on the ICIQ-OAB), and PD motor symptom severity (MDS-UPDRS < 33 on the part 3 motor score)⁵⁹. Participants will be randomized through computer-generated block randomization in groups of six. Based on preliminary data showing these cut points approximate the means among our randomized participants, we do not anticipate four stratification variables will present a challenge to recruitment. While participants will not be blinded to treatment group, the interventionist will be blinded to the participant's performance on the neuropsychological tests and SRTT performance.

Data Management: Participants' assessment data will be kept in a locked cabinet behind a locked door at each site of the Birmingham/Atlanta GRECC and the Richmond PADRECC. Bladder diaries will be scored by a research assistant who is blinded to the assigned treatment group. Data from the Birmingham and Richmond sites will be uploaded to a secure VA server in the form of PDF documents scanned on a VA device behind the VA firewall. Deidentified data will be entered and verified in Redcap by research staff at the Atlanta site, which will ensure accuracy of the data. A standard form will be used to record the date and reason for all

exclusions and dropouts, and these data will also be entered into the master database. Four times per year the PI will meet with the Atlanta-based data manager to review accrual, data entry, and eligibility criteria and examine the database for outliers or database entry errors at each site. The Redcap database will then be converted and data analyses will be completed in SAS 9.4 (SAS Institute, Cary, NC). Additional details regarding confidentiality of patient data are included in the Human Subjects plan.

Specific Aim #1: Using a RCT, determine non-inferiority of pelvic floor muscle exercise-based behavioral therapy versus drug therapy for urinary symptoms in PD.

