Rationale: The use of anticholinergic drugs for UI in PD, which are currently recommended by guidelines, increase polypharmacy and may add to the cognitive and autonomic burdens of PD. Impaired cognition and polypharmacy are recognized risk factors for medication non-adherence in PD and could lead to treatment failure for OAB⁶⁰. PFME-based behavioral therapy, while more labor-intensive, is free of drug side effects for patients. The PI's pilot studies demonstrate that adults with PD and UI can learn and implement PFME-based behavioral therapy resulting in significant decreases in UI and OAB symptoms. Given the efficacy of the URGE PD drug trial, a comparative effectiveness trial of behavioral therapy and drug therapy for bothersome urinary symptoms is a logical next step to better inform treatment guidelines for Veterans with PD. Based on our preliminary data showing similar effect sizes between behavior and drug therapy, a non-inferiority design is proposed. A non-inferiority design provides the most critical information needed to inform clinical guidelines without exposing additional participants to drug therapy. The reason for not including a behavior therapy plus drug condition is that we wish to disentangle the contributions of baseline levels of motor symptoms and cognitive scores on outcomes, hopefully gaining an understanding of which treatment might be more effective for which patients in light of the potential of drug side effects.

Intervention: Once randomized, both groups will participate in a 12-week study (**Figure 1**). Study visits (either in-clinic or via phone) will occur every two weeks for the first 8 weeks followed by a final in-clinic assessment at 12-weeks. Participants will be compensated \$50 upon completion of first visit procedures, \$50 for second visit procedures and \$60 for completion of visit 7 procedures with a maximum of \$160 for completion of all study visits (includes screening and follow-up visits).

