Self-assessed adherence to exercise or drug therapy will be assessed through questionnaires (both groups) and with exercise records or pill counts depending on group allocation. Data will be calculated as medians (and inter-quartile range), and compared using Kruskal-Wallis test for continuous variables or chi-square test (Fisher's exact when expected cell counts were <5) for categorical variables. Adverse event questionnaires will be administered at each in-clinic or phone visit after treatment allocation. The number of times a specific side effect is reported after the baseline assessment will be summed and presented as a continuous variable. Comparisons between groups of the proportion of participants reporting specific side effects will be performed by Fisher's exact test.

[Specific Aim #2 (mechanistic aim): Determine if domain-specific cognitive function impacts the response to exercise-based behavioral therapy or drug therapy for urinary symptoms.

Aim 2a: Do higher baseline motor skill learning capacity and executive function scores predict better outcomes in the exercise-based behavioral therapy versus drug therapy group?

Rationale: In spite of the potential for cognitive impairment, which occurs in up to 75% of PD patients within 10 years of diagnosis²⁹, some PD patients demonstrate evidence of neuroplasticity and benefit from learning motor skills as demonstrated through functional imaging studies^{30,31}. Understanding whether baseline domain-specific cognitive function is associated with successful implementation of behavioral therapy among adults with PD is important to understand the central control of bladder function and identify new targets to augment rehabilitation therapy in the setting of a neurodegenerative disease. While participants with significant cognitive impairment (MoCA < 18) will be excluded, this exclusion criterion will not eliminate participants with mild cognitive impairment. The range of MoCA scores among current completers of the BETTUR2 PD study (n=26) is 18 to 29 (mean=24.6 ± 2.9). Among the 11 participants randomized to behavioral therapy in the BETTUR2 PD study who had a MoCA score between 18-26 (includes the screening cutpoint for mild cognitive impairment in PD³⁷), the median reduction in weekly UI frequency eight weeks after randomization was 88% (IQR 42%-100%), suggesting that even mild cognitive impairment does not interfere with learning a behavioral therapy intervention.

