The neuropsychological assessment in the proposed study is a unique approach to further characterize domain-specific cognitive function as a predictor of the ability to use exercise-based behavioral therapy. The baseline neuropsychological battery will provide additional domain-specific measures of cognitive function (SRTT, executive function, word retrieval) that will be analyzed in the context of the ability to learn and implement the exercise-based behavioral strategy. These preliminary data will provide further evidence to support or refute the hypothesis that learning the PFME-based adaptive strategy is a procedural task and that implementation of the task uses implicit memory rather than explicit memory systems. Further, because several of the selected tests have neuroanatomical correlates, these data could support the design of future studies involving functional brain imaging to understand mechanisms of learning in the context of neurodegenerative disease, thus building on imaging studies in non-PD populations with OAB^{15,16}.

Measures: Participants in both groups will complete the SRTT (task of procedural learning) in addition to a neuropsychological battery that will include evaluations of executive function and explicit memory at baseline. These assessments mirror the evaluation included in the BETTUR2 study, which will ultimately increase the power of the evaluation to determine mediators impacting implementation of behavioral therapy for urinary symptoms in persons with PD.

Data Analysis: The analysis for Aim 2a will determine if baseline cognitive function scores mediate successful outcome in the behavioral therapy group. Based on previously published research and our pilot studies, successful implementation of behavioral therapy will be defined as achieving at least a 2-point reduction in the ICIQ-OAB symptom score^{24,61,64}. Cognitive function will be evaluated as a continuous and categorical measure (MoCA 18-24 vs 25-30).

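### Aim 2a asks whether baseline cognition predicts better outcomes with behavioral therapy versus drug therapy, but its analyses are framed on the behavioral arm and state no between-arm contrast

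*Combined protocol and SAP*

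**What the plan says.** **The question.** Aim 2a, in the Specific Aims and again in the Specific Aim #2 section, reads: "Do higher baseline motor skill learning capacity and executive function scores predict better outcomes in the exercise-based behavioral therapy versus drug therapy group". The parent aim names both treatments: "Determine if domain-specific cognitive function impacts the response to exercise-based behavioral therapy or drug therapy for urinary symptoms". The opening of Research Design and Methods says the baseline battery is there to "assess cognitive factors that may predict a preferred treatment strategy". The Aim 1 Rationale, explaining why there is no combination arm, wants to "disentangle the contributions of baseline levels of motor symptoms and cognitive scores on outcomes". It describes the benefit sought from this as "hopefully gaining an understanding of which treatment might be more effective for which patients in light of the potential of drug side effects".

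**The analysis.** The Aim 2a Data Analysis begins: "The analysis for Aim 2a will determine if baseline cognitive function scores mediate successful outcome in the behavioral therapy group". It then sets out:
- a success definition (a drop of 2 points or more on the ICIQ-OAB), stated for behavioral therapy;
- a comparison of baseline characteristics between responders and non-responders within the behavioral group;
- correlations of the SRTT and Wisconsin Card Sort scores with ICIQ-OAB change, introduced as change following behavioral therapy;
- a multivariable logistic model for success with behavioral therapy.

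Two sentences name no arm: the one on MoCA as a continuous and a two-category measure, and the closing sentence on correlations.

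**The data.** According to Aim 2a Measures and Table 7, both arms complete the baseline SRTT and battery, the MDS-UPDRS, and the ICIQ-OAB at baseline and week 12.

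**The concern.** A score can go with improvement in the behavioral arm for two different reasons. It may help patients use behavioral therapy in particular, or it may mark patients who do well on either treatment. Only the first bears on treatment choice, and only a comparison with the drug arm can separate the two.

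As written, a positive behavioral-arm result would invite the reading that patients with better cognition should prefer behavioral therapy, without evidence for it. The word 'mediate' adds to the confusion. A score measured before randomization cannot be changed by treatment, so it can be a predictor or an effect modifier but not a mediator.

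**Working it through.** The documents give no power, effect size or correlation for Aim 2a, so there is no figure of theirs to reproduce. The gap itself is found by reading the text; the numbers below show its consequence and what the fix can deliver.

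**1. Is a contrast supplied elsewhere?** No. Aim 2b does compare arms, but its outcomes are change in cognition and in motor score. The only effect modifier named in Aim 2 is the Anticholinergic Risk Scale, in Aim 2b. If the closing correlation sentence of Aim 2a were read as pooling both arms, one pooled correlation would still not answer a 'versus' question.

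**2. What can the one-arm analysis show?** Take 40 completers per arm (80 in the Power Analysis, two arms) and assume the same correlation of 0.5 in both arms, so that cognition favors neither treatment. Fisher z power within the behavioral arm is Φ(0.549 × √37 − 1.96) = Φ(1.38) = 92%. In simulation the behavioral-arm correlation was significant in 92% of trials, and the between-arm difference in about 5%.

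**3. Why the added model needs arm × motor score.** The SRTT asks participants to "press one of four keys on a response box which correspond to a lighted stimulus", so it may well track motor severity. Suppose the score has no effect, and motor severity predicts improvement in the behavioral arm only (standardized slope γ). If motor score enters as a main effect only, the false arm × score difference is γ × ρ × SD, where ρ is the score-motor correlation:
- γ = ρ = −0.3, SD 2.0: 0.09 × 2.0 = 0.18 points per SD of score.
- γ = ρ = −0.5, SD 2.0: 0.25 × 2.0 = 0.50 points per SD of score.

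In simulation the false difference was significant in 7% to about 20% of trials. With arm × motor score added, it averaged about 0 and was significant in about 5%.

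**4. What the added model delivers.** Assumptions not in the documents:
- SD of improvement 2.0. Table 6 uses 1.0 to 3.0, but for the 12-week score.
- Score-improvement correlation r in the behavioral arm and 0 in the drug arm.
- ρ of −0.3 or −0.5, and no motor effect on outcome.
- Normal scores and two-sided 0.05.

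The model has seven coefficients, so 80 − 7 = 73 df and t = 1.993.
- Average residual variance: s² = SD² × [(1 − r²) + 1] / 2.
- Variance of the slope difference: 2s² / [(n − 4)(1 − ρ²)], with n − 4 = 36.

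Example, r = 0.4: s² = 4 × (0.84 + 1) / 2 = 3.68, and the true difference is 0.4 × 2.0 = 0.8 points per SD.
- ρ = −0.3: variance 7.36 / 32.76 = 0.225, SE 0.474, half-width 0.94, power about P(Z > 1.993 − 0.8/0.474) = 38%.
- ρ = −0.5: variance 7.36 / 27 = 0.273, SE 0.522, half-width 1.04, power about 32%.

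| r vs 0 | True difference | 95% CI half-width | Power, formula | Power, simulated |
|---|---|---|---|---|
| 0.3 | 0.6 | 0.96-1.06 | 19-23% | 20-24% |
| 0.4 | 0.8 | 0.94-1.04 | 32-38% | 32-39% |
| 0.5 | 1.0 | 0.92-1.02 | 49-57% | 49-57% |

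Half-widths scale with the SD of improvement: about 0.5 points at SD 1.0 (half) and 1.4 to 1.6 at SD 3.0 (times 1.5).

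**The case against.** **The one-arm focus is deliberate.** Aim 2 is labelled mechanistic. The Aim 2a Rationale concerns whether the exercise strategy is learned through implicit memory, and the Measures section mirrors an earlier behavioral study so that power for that question grows. This stands. A reader might infer that the within-arm analyses are wrong or should be demoted; the documents do not support that, because those analyses address a stated hypothesis of their own. What the objection does not do is answer the 'versus drug' wording of the aim.

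**The treatment-choice language is tentative.** It uses 'may' and 'hopefully', and the neuropsychological and Aim 2a sections speak of exploratory analyses and preliminary data. This also stands, and keeps the point minor.

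**Power is too low for an interaction to help.** It is low, and a half-width near 1 point is wide beside the 2-3 point reductions cited in the Power Analysis. That argues for an estimate with its interval, or for rewording the aim. It does not make a one-arm analysis able to answer a two-arm question.

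**Conclusion.** The mismatch is real. Followed as written, the Aim 2a analyses give no estimate of whether cognition predicts benefit differently by treatment, although both arms provide the data. This conclusion rests on the text alone. The precision and power figures rest on the assumed correlations and SD of improvement.

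Three stronger readings are not supported. A reader might infer that the plan never compares the arms on cognition, but Aim 2b does so with cognition as an outcome, and that part of treatment choice is unaffected. A reader might infer that every Aim 2a sentence excludes the drug arm, but two sentences name no arm; they simply supply no contrast. And a reader might infer that the trial is too small and must grow, but the documents claim no power for Aim 2a, and an exploratory estimate needs no new sample size.

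This is a minor issue in an exploratory aim. Aim 1 is not affected.

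**What to change.** Either of two changes resolves it.

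**Option 1: add the comparison.** Specify an exploratory linear model of week-12 ICIQ-OAB, with both arms as randomized. Terms: arm, baseline ICIQ-OAB, baseline MDS-UPDRS part 3, score, arm × score, and arm × MDS-UPDRS part 3.
- Fit it once for SRTT and once for card-sort perseverative errors, with continuous MoCA as a supportive fit.
- Include everyone with a week-12 score and report the number missing per arm.
- Report each arm's slope and the difference with a 95% CI, and state in advance that a null interaction will not be read as showing that cognition is irrelevant to treatment choice.

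**Option 2: narrow the question.** Reword Aim 2a as prediction within the behavioral arm. Remove the claim that baseline cognition will indicate the preferred treatment (Research Design and Methods, and the cognition part of the Aim 1 Rationale). Leave the treatment-choice purpose that Aim 2b serves.

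Under either option, keep the within-arm analyses as planned and call baseline scores predictors or effect modifiers, not mediators.

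**Cost.** Text only, with no new data, visits or participants. The price of Option 1 is an imprecise result. The arm × motor score term also widens the interval: at a score-motor correlation of −0.5, the half-width rises from about 0.9 to 1.0-1.06 points.

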To explore other potential characteristics of successful behavioral therapy implementation, we will examine baseline characteristics that differ between those in the behavioral therapy group who demonstrate at least a 2-point improvement (reduction) in ICIQ-OAB symptom score versus those who report less improvement. Baseline characteristics will include gender, age, PD severity as measured by the MDS-UPDRS motor part 3 score (mild vs. moderate), depression as well as the pre-specified measures of cognitive function (SRTT and Wisconsin Card Sort Test). Baseline characteristics will be compared using chi-square or t-tests as appropriate.

We will examine the correlation between cognitive function tests of procedural learning and executive function with change in ICIQ-OAB score after behavioral therapy. Performance on the SRTT will be assessed as the mean change in time (milliseconds) between random and sequential tasks. Performance on the Wisconsin Card Sort Test will be assessed using the perseverative errors score. We will correlate these measures with the change in ICIQ-OAB score between baseline and 12-weeks post-randomization.

Baseline characteristics which are significantly associated with successful implementation of behavioral therapy will be included as part of a multivariable logistic regression model including SRTT performance, Wisconsin Card Sort Test perseverative errors score in order to determine if these cognitive domains are important in the central nervous system control of OAB symptoms in response to behavioral therapy.

Aim 2b: Compared to exercise therapy, does anticholinergic drug treatment for urinary symptoms worsen executive function and PD motor symptom severity?

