To assess the potential impact on motor symptoms, we will assess the change in the motor symptom subscale of the MDS-UPDRS (part 3 score). Similar to the cognitive testing, baseline and 12-week post-randomization assessments will be evaluated using paired t-tests to assess for change within the drug group and two-sample t-tests for difference across groups, with the behavioral therapy group serving as a control for this analysis. Previous research suggests an increase in the MDS-UPDRS part 3 score of 4.6 points is associated with clinically relevant decline in motor function⁷⁰.

Visit Schedule

Visit 1: Baseline (One phone/telehealth session and one in-person session)

Explanation of study procedures and consent to be a participant

Interview: Demographics, continence and medical history, MoCA, LSA, GDS

Physical: Height, weight, vital signs, cardiac, pulmonary, and abdominal exam, genital and rectal exam, basic neurologic exam, MDS-UPDRS, determination of post-void residual by bladder ultrasound

Laboratory Examination: Urinalysis and BMP and HgbA1c if indicated

Education: How to complete bladder diary, handout take-home questionnaires (ICIQ-OAB and OAB-QOL)

Visit 2 (Part 1) : Randomization

Interview: Collect and review 7-day bladder diary, ICIQ questionnaires

Physical: Vital signs; review laboratory results; determination of post-void residual by bladder ultrasound if not conducted at first visit;

Procedure: **Randomization (Behavioral Therapy or Drug Therapy)**

Behavioral Therapy	Drug Therapy

Visit 2 (Part 2): Behavioral Therapy Randomization
 
Procedure: Neuropsychological battery, SRTT, Pelvic floor muscle exercise training
 
Education: specific behavioral techniques for constipation, modification of fluid intake or timed voiding
	
Visit 2 (Part 2) : Drug Therapy Randomization
 
Procedure: Neuropsychological battery, SRTT
 
Education: Medication

Visit 3: Behavioral Therapy (2 weeks)
 
Interview: Review PFME record, address new problems, reinforce practice at home and verbal feedback regarding muscle control
 
Education: Urge suppression strategy, management of stress-related urine loss (if applicable)
	
Visit 3: Drug Therapy (2 weeks)
 
Interview: Medication Management, Medication Side Effects
 
Education: Medication & Bladder Diary & Forms (to return at Visit 5)

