Human Subjects Involvement and Characteristics: Men and women with PD recruited from the Atlanta, Birmingham, Richmond, and Philadelphia VAMCs as well as in the surrounding community. We propose randomizing 90 participants to either exercise-based behavioral therapy or drug therapy with Solifenacain. In order to complete the study in 80 participants, we anticipated having to screen approximately 180 PD patients to identify those with clinically significant OAB symptoms, and enroll approximately 45 participants in each group. These estimates are based on our experiences in the BETTUR PD and BETTUR2 pilot studies. In the BETTUR PD study, 33 individuals were screened to enroll 20 participants. Of the 20 participants who were enrolled, 17 completed the study demonstrating a 15% drop out rate once enrolled. To date, in the BETTUR2 study, we have screened 107 individuals to randomize 51 participants and have had 6 participants drop out (11.7% rate).

During FY16, 541 unique Veterans with PD were served by the Atlanta VA and surrounding CBOCs. For the BETTUR PD pilot, 14 of the 32 screened subjects were recruited from the Atlanta VA after mailing letters to 360 Veterans identified with a diagnosis of PD in the Metro Atlanta area in FY08. Recruitment was extended to a university-based movement disorders clinic to achieve the intended sample size of 20 enrolled subjects. For the BETTUR2 study, of the 65 persons who have undergone screening procedures thus far, 25 were Veterans and 40 were recruited from university-based movement disorders clinics in Atlanta and Birmingham in order to maximize the team's ability to recruit the intended sample size. Thus, we propose to recruit both Veterans and non-Veterans for the proposed study from the outset. The university affiliates in Atlanta (Emory), Birmingham (University of Alabama at Birmingham), Richmond (Virginia Commonwealth University), Philadelphia (University of Pennsylvania) all have active movement disorders programs, which enhance the overall resources available to the study.

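### Aim 2a uses baseline motor severity only as mild versus moderate although the full MDS-UPDRS part 3 score is collected; the continuous score would be more informative at no cost

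*Combined protocol and SAP*

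**What the plan says.** The Data Analysis text for Aim 2a compares "those in the behavioral therapy group who demonstrate at least a 2-point improvement (reduction) in ICIQ-OAB symptom score" with behavioral-arm participants who improve less. Among the characteristics compared is "PD severity as measured by the MDS-UPDRS motor part 3 score (mild vs. moderate". The method is given in one sentence: "Baseline characteristics will be compared using chi-square or t-tests as appropriate". Characteristics that are significant in this comparison join a multivariable logistic model that also holds SRTT performance and the Wisconsin perseverative-errors score.

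Aim 2a gives no number for the mild/moderate boundary. The only cut in the plan is under Randomization, where a stratum is defined by "MDS-UPDRS < 33 on the part 3 motor score". That section adds that, in preliminary data, "these cut points approximate the means among our randomized participants".

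The full score is available. Table 7 lists the MDS-UPDRS at baseline and 12 weeks, and the Aim 2b analysis uses it numerically: "we will assess the change in the motor symptom subscale of the MDS-UPDRS (part 3 score". Aim 2a itself handles MoCA both as a continuous and as a categorical measure, but gives the motor score only the categorical form.

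**The concern.** Cutting a measured score in two treats everyone on the same side of the cut as alike. In a sample of about 40 that is a noticeable loss. A real association between motor severity and response to behavioral therapy becomes easier to miss.

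There is a second consequence. The rationale for Aim 1 says the design is meant to separate the contributions of motor symptoms and cognition to outcome. Motor severity must pass a significance screen to enter the logistic model, so a weaker test makes it more likely to be left out. If the two-level factor does enter, motor differences within each half remain unadjusted.

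The cut has a clear use as a randomization stratum. Aim 2a's success-versus-failure comparison lies within one arm, so matching the stratum gives no reason to use the split there, and the plan offers no other.

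**Working it through.** The plan states no effect size, success rate, alpha or power for Aim 2a, so there is no stated figure to reproduce.

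**Inputs from the plan**
- Sample: 90 randomized and 80 completing, so 80 / 2 = 40 behavioral completers. Human Subjects says the trial will "enroll approximately 45 participants in each group". Only the count is used here, not the primary power calculation behind it.
- Position of the cut: 33, near the pilot mean (Randomization), so roughly a 50:50 split.

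**Assumptions, not in the plan**
- Two-sided 0.05 test, and an approximately normal part 3 score.
- Success in 50% or 60%. The pilots saw mean reductions of 2 to 3 points and success is a reduction of at least 2, so half or somewhat more is plausible.
- Standardized difference *d* in motor score between successes and failures: 0.6, 0.8 or 1.0, with smaller values also tried.

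**Information kept.** For a normal score cut at its mean, the correlation between the score and its split is φ(0) / √(0.5 × 0.5) = 0.399 / 0.5 = 0.798. Its square is 2/π = 0.637. The split therefore carries about 64% of the information and leaves 36% of the score's variance within the two halves. For this one test, 40 people do the work of about 40 × 0.637 = 25.

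**Closed-form power.** For a correlation *r*, power ≈ Φ(√(n − 3) × atanh(r) − 1.96), with √37 = 6.083. The split replaces *r* by 0.798*r*.
- *r* = 0.3: 47% with the score, 32% with the split; loss 15 points.
- *r* = 0.4: full score, 6.083 × 0.424 − 1.96 = 0.62, giving 73%; split (*r* = 0.319), 6.083 × 0.331 − 1.96 = 0.05, giving 52%; loss 21 points.
- *r* = 0.5: 92% against 73%; loss 19 points.

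**Simulated power** (n = 40, 3,000 samples per row, t-test on the score against uncorrected chi-square on the split):

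| d | Success | t-test | Chi-square | Loss (points) |
|---|---|---|---|---|
| 0.6 | 50% | 44.9% | 28.7% | 16.2 |
| 0.6 | 60% | 44.2% | 31.3% | 12.9 |
| 0.8 | 50% | 69.2% | 48.5% | 20.7 |
| 0.8 | 60% | 67.4% | 49.8% | 17.6 |
| 1.0 | 50% | 86.9% | 67.6% | 19.3 |
| 1.0 | 60% | 85.3% | 67.6% | 17.7 |

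The loss is thus about 13 to 21 points. It is about 2 to 8 points for *d* = 0.3 to 0.4 and reaches about 12 at *d* = 0.5. With 70% success it is 9 to 18 points for *d* = 0.6 to 1.0.

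**Effect on the screen.** If the screen is the same 0.05 test, the chance of leaving motor severity out is 100% minus the power. At *d* = 0.6 that is 69 to 71% with the split and 55 to 56% with the score. At *d* = 0.8 it is 50 to 52% against 31 to 33%.

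**Adjustment, if the factor is kept.** A large-sample logistic simulation assumed an SRTT-motor correlation of 0.3 to 0.7 and no true SRTT effect. Adjusting for the split left about 38 to 52% of the bias in the SRTT coefficient; adjusting for the continuous score left about none. The correlation is an assumption, so this shows a mechanism and does not estimate a bias in this trial.

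**The case against.** The strongest reply is that this is one secondary covariate in a paragraph framed as exploratory. The Aim 2a cognitive predictors, SRTT and perseverative errors, stay continuous and are also correlated with continuous change in the ICIQ-OAB score. That is right, and it limits the point to a minor improvement. A reader might take the 13 to 21 points as a loss for Aim 2a as a whole, or as holding whatever the effect. The documents support neither: the loss belongs to the motor-severity test alone, and the plan gives no effect size that would fix its magnitude.

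A reader might also infer that the two-level factor is certain to sit in the logistic model. It is not; entry depends on the screen. For the same reason, changing the form of the variable does not by itself secure control of motor severity. At *d* = 0.6 even the continuous score would fail the screen more often than not.

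A third tempting reading is that SRTT findings will be contaminated by motor slowness. The plan scores SRTT as the difference between random and sequential times, which removes a constant motor-speed component. Some dependence could remain, for instance if slowing is proportional, but the documents give no SRTT-motor correlation, so a bias cannot be asserted.

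Finally, the Randomization section supports its cut with a cited study of severity levels on this scale, so mild/moderate may be a recognized classification. That supports the stratum and descriptive use; it does not make the split the better predictor within one arm. Nor is the numeric use in Aim 2b a contradiction, since there the score is a change outcome. It shows only that the full score is at hand.

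**Conclusion.** The point holds as a minor, cost-free improvement to an exploratory analysis. Splitting the part 3 score keeps about 64% of its information if the score is near normal and the cut near its mean. With about 40 behavioral completers and a two-sided 0.05 test, the cost to this one covariate is about 13 to 21 points of power for an assumed *d* of 0.6 to 1.0 with 50 to 60% success, and about 2 to 12 points for smaller effects. The split also makes motor severity more likely to be screened out of the logistic model and, if retained, only partly controlled. Whether that would bias the SRTT coefficient, and by how much, cannot be settled from the documents.

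**What to change.** In the Aim 2a Data Analysis text, replace the two-level motor variable with the continuous score, for example:

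> Baseline motor severity will be analyzed as the continuous MDS-UPDRS part 3 score, compared between successes and failures by t-test. The same continuous score will be the motor term in the logistic model and will be included whether or not it is significant in the bivariable comparison.

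The last clause is needed only if control of motor severity is intended, and that should be decided before outcome data are examined. Keep the cut at 33 for stratification and description.

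The change takes a few words, with no new data or visits. Swapping the form of the variable adds no model parameter. Including it regardless of the screen commits one term: with 50 to 60% success there would be 40 × 0.5 = 20 to 40 × 0.4 = 16 failures, so a model with SRTT, perseverative errors and motor score has about 16 / 3 = 5 to 20 / 3 = 7 failures per term. That leaves little room for further covariates.
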